Cervical cancer screening strategies are most effective when based on local evidence and tailored to the population and resource infrastructure.^{xxiii,xxiv} Available screening tests include HPV testing, cytology [liquid-based or Pap smear], and VIA. HPV testing has a high sensitivity (93-100%) and specificity (80-90%), but low PPV (12-23%) for pre-invasive disease.^{xxv,xxvi,xxvii,xxviii} Cytology is operator dependent, with variable sensitivity (43-94%) and specificity (78-98%), but PPV of up to 90%.^{xxix,xxx,xxxI} VIA sensitivity (17-100%) and specificity (8-95%) also are variable, and in resource-poor settings without HPV testing or histopathology can reduce cervical cancer mortality.^{xxxii,xxxiii,xxxiv} There is increasing evidence that primary HPV testing is the most effective screening strategy.^{xxxv,xxxvi,xxxvii,xxxviii} Primary testing with HPV alone, followed by treatment, creates a high likelihood of overtreatment and harm to women who desire future fertility. In addition, primary HPV testing followed by colposcopy is not feasible in settings like Botswana where there are an insufficient number of trained colposcopists. To address these two issues, two-stage screening strategies, consisting of HPV testing followed by either cytology or VIA, have been advocated.^{xxxix,xl,xli} HPV testing followed by cytology results in increased sensitivity and specificity.^{xlii} In a single study from Cameroon in a population with a high prevalence

of HIV (14.2%), HPV testing followed by Pap smear has been shown to have superior sensitivity and specificity compared to HPV testing followed by VIA.^{xliii}

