The proposed study will enroll 300 women for HPV testing in order to evaluate 81 HPV-positive women (see Sample Size calculations below). The first 100 enrollments will be nested within an existing cross-sectional pilot study designed to determine the uptake, acceptability, and feasibility of testing women for HPV using self-collected samples. The goal of this 100-person pilot study is to inform the future scale-up of primary HPV screening, by answering the question of whether self-collected swabs are as good as provider-collected swabs. These 100 participants will self-collect a vaginal specimen and undergo a concomitant provider-collected specimen for HPV testing; a provider-collected approach will be used for the subsequent 200 women who enroll for this proposed study. Co-enrollment with the existing pilot study leverages the existing study and facilitates use of the same staff and resources to ultimately accrue 300 women at minimal cost.

Research question

Which two-stage cervical cancer screening algorithm is more effective for HIV-positive women in Botswana: HPV followed by Papanicolaou (Pap) smear or HPV followed by visual inspection with acetic acid (VIA)?

Study Procedures

[figure not shown]
For all 300 participants, HPV testing will be performed with either the commercially-available Cepheid Xpert[®] HPV Assay or the commercially-available Roche Cobas[®] HPV Assay for provider- and participant-collected samples, as per the protocol of the HPV pilot study. The pilot study currently utilizes a Cepheid GeneXpert machine on loan from the National Health Laboratory (NHL), and the duration of its availability is unknown. Should the GeneXpert machine become unavailable, the Roche Cobas[®] machine at the NHL will be used for HPV testing. After the HPV pilot study ends, the remaining 200 participants will be enrolled and screened in a similar manner using a provider-collected approach. This study introduces Pap smear collection for all participants at the time of provider-collected HPV specimen. Pap smear will be prepared using standard technique at the site of collection.

Participants who test HPV-negative will have their Pap smear sent to the NHL for staining and pathologist evaluation. If the Pap smear is abnormal, they will be referred to colposcopy per current Botswana Cervical Cancer guidelines.

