The goal of a two-stage algorithm is to increase PPV while maintaining sensitivity and specificity, and thus reduce overtreatment. Sample size assumptions were based on preliminary data, existing literature, and patient behavior regarding clinical follow-up. Among the first 25 women recruited in the parent study, the incidence of HPV-positivity was 30%. In a population with relatively high HIV prevalence, the PPV of an HPV-positive test for high-grade cervical dysplasia was 24%.^{xlvi} Our sample size calculation was targeted to detect an improvement in PPV of 25% between HPV testing alone and either two-stage algorithm (a PPV of 49% for the two-stage algorithms). Assuming a two-sided test and an alpha of 0.05, a sample size of 81 participants will yield over 80% power to detect the specified difference. Clients receiving care at the Infectious Disease Care Clinic (IDCC) tend to return for clinical follow-up appointments, because they come to IDCC each month to obtain their free anti-retroviral medications. Clients seeking care at the gynecology outpatient clinic may be less integrated into routine care. Thus, we anticipate that approximately 10% of HPV-positive participants will not return for colposcopy. The proposed study will aim to enroll 300 participants to yield 90 who are HPV positive 81 of whom we expect to return for colposcopy.

Data analysis

All data will be analyzed using SAS 9.4 (Cary, NC) at Beth Israel Deaconess Medical Center. Descriptive statistics will be presented as mean with standard deviation, median with interquartile range, or proportion, based on data type and distribution. Data will be compared using the appropriate parametric or non-parametric test for continuous variables and Chi-square or Fisher's exact test for categorical variables. All tests will be two-sided and a p-value <0.05 will be considered statistically significant.

We will calculate sensitivity, specificity and PPV of HPV/Pap smear and HPV/VIA to detect high-grade cervical dysplasia amongst HPV-positive participants. We will also evaluate associations between HPV type, cytology, VIA result, and histopathology results.

C. Subject Selection

Inclusion and Exclusion Criteria

Inclusion criteria for the study are:

- 1) ≥ 25 years of age
- 2) HIV-positive
- 3) Competent to understand study procedures and give informed consent.

Exclusion criteria are:

- 1) Currently pregnant (as diagnostic procedures for cervical cancer are often deferred during pregnancy)

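### Does the claim of over 80% power with 81 women fail because the two-stage PPV rests on only a part of them?

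*Combined protocol and SAP*

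**What the plan says.** B3.A plans to "enroll 300 women for HPV testing in order to evaluate 81 HPV-positive women". B3.B, Sample Size, derives the same 81 from 300 enrolled, 30% HPV-positive and 10% of those not returning. It opens with the premise "The goal of a two-stage algorithm is to increase PPV while maintaining sensitivity and specificity" and continues: "Our sample size calculation was targeted to detect an improvement in PPV of 25% between HPV testing alone and either two-stage algorithm". The rates are 24% and 49%, two-sided at alpha 0.05, with the conclusion that "a sample size of 81 participants will yield over 80% power to detect the specified difference".

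B3.B, Data analysis, gives three relevant statements. For categorical data in general it names "Chi-square or Fisher's exact test for categorical variables". For the aims: "We will calculate sensitivity, specificity and PPV of HPV/Pap smear and HPV/VIA to detect high-grade cervical dysplasia amongst HPV-positive participants". And in addition: "We will also evaluate associations between HPV type, cytology, VIA result, and histopathology results".

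Under B3.A every HPV-positive woman who returns has a Pap result and a VIA result before colposcopy, so each two-stage PPV comes from a subset of the same 81 women.

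**The concern.** The power sentence reads as though 81 women supply each PPV. They supply only the one for HPV alone. The two-stage denominator is the triage-positive women, whose number depends on a triage sensitivity the plan does not give. Data analysis also never lists HPV alone against two-stage as a comparison, so no test is tied to the one contrast that was powered.

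Two things could be at stake. If an analyst set triage-positive women against all 81 as though they were separate groups, the overlap would make the test very conservative and cost power. And a reader who took 81 as the two-stage denominator would expect a tighter PPV estimate than the study can give.

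**Working it through.** **Inputs.** From B3.B: N = 81, PPV of HPV alone p = 0.24, two-stage PPV v = 0.49, two-sided alpha 0.05. Triage sensitivity among HPV-positive women, s, is not in the plan and is varied here as an assumption.

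**The plan's figures.** Enrolment: 300 x 0.30 = 90, and 90 x 0.90 = 81. Power with two independent groups of 81, pooled rate 0.365:
- SE under the null = sqrt(2 x 0.365 x 0.635 / 81) = 0.0757
- SE under the alternative = sqrt((0.24 x 0.76 + 0.49 x 0.51) / 81) = 0.0731
- z = (0.25 - 1.96 x 0.0757) / 0.0731 = 1.39, so power is 92%

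This satisfies the inequality, but 81 cannot be the two-stage denominator at these rates.

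**Two-stage denominator.** Expected high-grade cases: 81 x 0.24 = 19.44. Expected triage-positives: 19.44 x s / 0.49 = 39.7 x s, so 39.7 at most.

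**A valid test.** Let f be the triage-positive fraction and q the high-grade prevalence in triage-negative women. Since p = f v + (1 - f) q,

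v - p = (1 - f)(v - q).

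Equal PPVs therefore means equal prevalence in triage-positive and triage-negative women, which are disjoint groups. Check at s = 0.80: f = 31.7/81 = 0.392, q = 3.89/49.26 = 0.079, and 0.608 x 0.411 = 0.25, the planned difference.

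**Power of that test.** Exact, by enumerating all 95,284 possible tables of 81 women (true and false positives and negatives of triage):

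| Triage sensitivity | Expected triage-positives | Prevalence in triage-negatives | Chi-square | Fisher |
|---|---|---|---|---|
| 80% | 32 | 7.9% | 99% | 99% |
| 70% | 28 | 11.0% | 97% | 95% |
| 60% | 24 | 13.6% | 91% | 89% |
| 50% | 20 | 15.9% | 83% | 78% |
| 43% | 17 | 17.3% | 75% | 70% |

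Power reaches 80% at a sensitivity of about 47% (chi-square) or 51% (Fisher). Type I error is 4.9-5.1% for chi-square and 3.3-3.7% for Fisher.

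**Overlapping groups.** Triage-positives against all 81 as if independent, by chi-square: 87%, 71% and 62% power at sensitivities of 80%, 60% and 50%. It reaches 80% at a sensitivity of 71% (79% for Fisher). Its chi-square type I error is only about 0.1-1.4%, which explains the loss.

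**Precision.** The 95% half-width is 1.96 x sqrt(0.49 x 0.51 / n): 15.5 points at n = 40, 17.3 at 32, 20.0 at 24, and 10.9 at 81.

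**The case for a change.** The strongest case for a change is that the condition behind the power figure is unstated and not trivially met. The 47-51% threshold lies inside the background range for cytology in B2, "Cytology is operator dependent, with variable sensitivity (43-94%) and specificity (78-98%), but PPV of up to 90" per cent, and inside that for VIA (17-100%). At 17% sensitivity with PPV held at 49%, nested chi-square power is only 38%. The goal of maintaining sensitivity carries no number, and one sentence could link the powered contrast to a test.

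Part of this stands: the sensitivity and the link are indeed unstated. The rest carries less weight.

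- The B2 ranges describe stand-alone tests, not triage of HPV-positive women, and each sensitivity comes with its own specificity. A sensitivity of 43% with 90% specificity gives a PPV of 0.1032 / (0.1032 + 0.0760) = 58% and 88% power. With 78% specificity it gives 0.1032 / (0.1032 + 0.1672) = 38% and 44% power, but that is no longer the targeted effect.
- Among HPV-positive women, HPV testing alone detects every case by construction. A triage sensitivity of 50% would therefore halve the sensitivity of HPV testing alone, the opposite of the stated goal.
- The overlapping-groups test is not in the plan. It arises only by joining the Sample Size contrast to a general sentence about categorical data, so its 71-79% thresholds describe a hypothetical error.
- Another reading, an exact one-sample test of the two-stage PPV against the literature value of 24%, has about 84% power at 80% sensitivity and 79% at 70%. It too depends on sensitivity, but it shows that the unnamed test is not confined to the two readings above.

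The point on precision is correct. It follows, however, from the definition of PPV: the analysis must divide by the triage-positive women, and the observed count will show how many there were.

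**Conclusion.** No change follows. The two-stage PPV does rest on at most about 40 expected women, and the plan leaves the triage sensitivity and the test for the powered contrast unstated. But the power claim is not shown to be wrong. With the planned association of cytology or VIA with histopathology, tested by the planned chi-square or Fisher's exact test among HPV-positive women, power exceeds 80% for any triage sensitivity above about 47-51%, and is 95-99% at 70-80%.

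The aims in B1 are to estimate sensitivity, specificity and PPV; the contrast with HPV alone appears only as the basis for the sample size. Supplying the missing detail would leave enrolment, procedures and estimates as they are.

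This rests on the plan's own 24%, 49% and 81, on an analyst comparing disjoint rather than overlapping groups, and on reading the goal of maintaining sensitivity as ruling out a triage test that misses about half of the high-grade lesions.

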PART B STUDY DESCRIPTION

TITLE OF PROTOCOL	Development of a two-stage cervical cancer screening algorithm for Botswana
Principal Investigator	[name]

B1. PURPOSE OF PROTOCOL

Cervical cancer screening programs vary across settings and there is no clear guidance for effective screening programs for HIV-positive women. Evaluating the performance of algorithms that include human papillomavirus (HPV) DNA testing as first stage screening in high HIV prevalence settings like Botswana is essential for establishing an evidence-based strategy for cervical cancer screening in HIV-positive women. The proposed study seeks to evaluate sensitivity, specificity, and positive predictive value (PPV) of two different two-stage cervical cancer screening algorithms for HIV-positive women in Botswana: HPV followed by Papanicolaou (Pap) smear, and HPV followed by visual inspection with acetic acid (VIA). The specific aims are:

1. To determine the sensitivity, specificity, and PPV of a two-stage screening algorithm that utilizes HPV testing followed by Pap smear for the detection of high-grade cervical dysplasia, using colposcopy with histology as the gold standard.
2. To determine the sensitivity, specificity, and PPV of a two-stage screening algorithm that utilizes HPV testing followed by VIA for the detection of high-grade cervical dysplasia, using colposcopy with histology as the gold standard.

B2. SIGNIFICANCE AND BACKGROUND FOR THE STUDY

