Cervical cancer is the fourth leading cause of cancer death in women worldwide and is the leading cause of cancer death in women in Botswana.^{i,ii,iii} The disease burden in Botswana is impacted by the high prevalence of HIV (22% among people aged 15-49 years), which is a well-established risk factor for cervical cancer.^{iv,v,vi} Cervical cancer is largely preventable and treatable where screening programs and treatment are available.^{vii,viii,ix,x} The majority of cervical cancers are associated with infection with high-risk HPV subtypes (HPV).^{xi,xii,xiii} Among HIV-positive women, persistent HPV positivity and infection with multiple subtypes are strong risk factors for cervical cancer.^{xiv} HPV prevalence is variable, ranging from 15-45%, with higher prevalence in HIV-positive women.^{xv,xvi,xvii} HPV 16, 18, and 45 are the high-risk subtypes most commonly associated with cervical cancer in Africa. In Botswana, HPV subtype prevalence in HIV positive women with high grade precancerous cervical lesions include 16, 18, 35, 58, 61; infections with multiple subtypes is common.^{xviii,xix,xx,xxi,xxii}

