- 2) Currently menstruating or having persistent vaginal discharge
- 3) Previous hysterectomy
- 4) Previous diagnosis of cervical cancer

B4. POSSIBLE BENEFITS

Participants will benefit from this study by being tested for HPV, which is a test not currently available in regular care in Botswana. Participants who test positive for HPV may be identified as at higher risk for cervical cancer earlier than standard care, which may allow for more timely management.

Potential benefits to Botswana include determination of the effectiveness of two-stage screening algorithms for cervical cancer. Two-stage screening strategies have been widely adopted in other settings as they increase the specificity and positive predictive value of pre-invasive cervical disease, and thus reduce over-treatment of insignificant screening findings. The study will provide valuable operational data as the country prepares to scale up HPV testing as part of its Comprehensive Prevention and Control Strategy. Finally, study results will serve to estimate the prevalence of HPV subtypes, which may inform HPV vaccination policies and assessments.

B5. POSSIBLE RISKS AND ANALYSIS OF RISK/BENEFIT RATIO

The potential risks encountered during the study are: 1) HPV screening, 2) Sample collection, 3) Colposcopy and 4) Loss of confidentiality

1) HPV screening: The major risk for participants in this study is the concern and worry they might experience while awaiting HPV test results. Participants will receive counseling before and after HPV screening to answer questions that they may have or allay any worries. Participants who test positive for HPV might feel uncomfortable, anxious or depressed about their result and there may be stigma associated with their diagnosis. Trained personnel will give counseling to both participants and their partners to assist with any of these issues. All participants with HPV infection will receive standard of care follow-up and treatment as outlined.

2) Specimen collection: There may be some temporary discomfort associated with self-collected and provider-collected vaginal swabs. Study personnel will be trained how to minimize any adverse events and any such event that occurs will be reported to both the Site Coordinator and the Principal Investigator.

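### Aims 1 and 2 ask for the accuracy of the two-stage algorithms, but the analysis uses HPV-positive women only, so it measures triage accuracy and understates algorithm specificity

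*Combined protocol and SAP*

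**What the plan says.** B1 (Purpose of Protocol) defines the target of each aim as the algorithm. Aim 1 reads "To determine the sensitivity, specificity, and PPV of a two-stage screening algorithm that utilizes HPV testing followed by Pap smear", and Aim 2 asks for the same three measures for "a two-stage screening algorithm that utilizes HPV testing followed by VIA". The reference standard in both is colposcopy with histology.

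The only accuracy analysis is in B3.B, Data analysis: "We will calculate sensitivity, specificity and PPV of HPV/Pap smear and HPV/VIA to detect high-grade cervical dysplasia amongst HPV-positive participants". Under the study procedures in B3.A, HPV-negative women have one study visit and are referred to colposcopy only if their Pap smear is abnormal. No section counts them as algorithm-negative or says that the estimates describe the triage step.

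On purpose, B3.B (Sample Size) says: "The goal of a two-stage algorithm is to increase PPV while maintaining sensitivity and specificity, and thus reduce overtreatment". B4 says of two-stage strategies used elsewhere that "they increase the specificity and positive predictive value of pre-invasive cervical disease". The research question in B3.A is "Which two-stage cervical cancer screening algorithm is more effective for HIV-positive women in Botswana".

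**The concern.** Within the HPV-positive subset every woman has passed the first stage. A positive HPV/Pap result there is a positive Pap smear, and a positive HPV/VIA result is a positive VIA. The planned figures would carry the algorithms' names but measure the second test alone.

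This affects specificity most. The algorithm's false positives should be set against all screened women without high-grade disease, most of whom are HPV-negative. The subset also has no usable comparator: among HPV-positive women, HPV testing alone has 100% sensitivity and 0% specificity by construction. Whether specificity is maintained or increased cannot be judged there.

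A reader would turn to a whole-population figure, such as the one in B2: "HPV testing has a high sensitivity (93-100%) and specificity (80-90%), but low PPV (12-23%) for pre-invasive disease". Set beside that, a triage specificity in the low seventies would suggest that adding a second stage loses specificity. That is impossible, because triage can only remove false positives. B10 says the results will go to the Ministry of Health to guide national programming.

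**Working it through.** **Plan's own figures.** 300 × 0.30 = 90 HPV-positive and 90 × 0.90 = 81 returning for colposcopy, as stated. For PPV 24% versus 49%, two independent groups of 81 at two-sided alpha 0.05 give 91.8% power, consistent with the stated figure of over 80%. That calculation concerns PPV and does not enter this point.

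**Inputs.**
- From B3.B, Sample Size: 300 screened, 90 HPV-positive, 210 HPV-negative; PPV of HPV alone 24%; target PPV 49%.
- From B2: HPV sensitivity 93-100%; cytology sensitivity 43-94% and specificity 78-98%; VIA sensitivity 17-100% and specificity 8-95%; HPV prevalence 15-45%.
- Assumed: triage sensitivity s among HPV-positive women, for which the documents give no design value. The B2 ranges are borrowed for it, with 80% as an illustration. No disease in HPV-negative women, relaxed below.

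**Formulas.**
- Among HPV-positive women, diseased D = 0.24 × 90 = 21.6 and not diseased 68.4.
- TP = s × 21.6; FP = TP × 0.51/0.49.
- Planned specificity = 1 − FP/68.4.
- Algorithm specificity = 1 − FP/(68.4 + 210) = 1 − FP/278.4.
- HPV-alone specificity = 210/278.4 = 75.4%.
- Gap = 0.754 × (1 − planned specificity), which is never negative.

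**Specificity at PPV 49%.**

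| s | FP | Planned | Algorithm | Gap (points) |
|---|---|---|---|---|
| 0.17 (VIA low) | 3.8 | 94.4% | 98.6% | 4.2 |
| 0.43 (Pap low) | 9.7 | 85.9% | 96.5% | 10.7 |
| 0.80 (illustration) | 18.0 | 73.7% | 93.5% | 19.8 |
| 0.94 (Pap high) | 21.1 | 69.1% | 92.4% | 23.3 |
| 1.00 (VIA high) | 22.5 | 67.1% | 91.9% | 24.8 |

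Planned specificity falls below 75.4% when s × 21.6 × (0.51/0.49)/68.4 exceeds 0.246, that is, when s exceeds about 0.75.

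**HPV prevalence.** At s = 0.80 and prevalence 15%, 30% and 45%, algorithm specificity is 96.9%, 93.5% and 89.9%. Planned specificity stays at 73.7%, so the gap runs from 23 to 16 points.

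**Cited specificities in place of the PPV target.** Cytology at 78-98% gives a gap of 0.754 × 0.22 = 16.6 points down to 0.754 × 0.02 = 1.5. VIA at 8-95% gives 0.754 × 0.92 = 69.4 down to 0.754 × 0.05 = 3.8.

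**Disease missed by HPV.** Missed cases m = D × (1/Se − 1), where Se is HPV sensitivity. At Se = 0.93, m = 1.6, or 0.8% of 210. Algorithm specificity at s = 0.80 is then 1 − 18.0/276.8 = 93.5%, unchanged to one decimal. Algorithm sensitivity is 0.80 × 0.93 = 74.4%, not 80%.

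**What does not change.** Every algorithm-positive woman is HPV-positive, so PPV is the same on either base. Both algorithms share the same first stage, so their order is preserved.

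**The case against.** The strongest reply is that the main decisions survive. The sample size targets PPV, the research question is Pap versus VIA, and neither is affected. No test of specificity against HPV alone is planned, and the B4 remark is about other settings. The restriction is also stated openly in the analysis sentence. All of this is true and limits the seriousness. But a disclosed denominator does not answer aims that ask for the algorithm's specificity and sensitivity.

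Second, the apparent loss of specificity is conditional. It needs the PPV target of 49% to be met and triage sensitivity above about 75%. If the cited cytology specificity of 78-98% is used instead, planned Pap specificity never falls below 75.4%, and falls short of the cited 80-90% for HPV only in the lower part of its range. That stands: the 73.7% versus 93.5% contrast is an illustration. The plan's inputs also imply an HPV specificity of 75.4%, below the 80-90% in B2, so the two comparators do not agree.

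Third, restricting to HPV-positive women keeps to those sent for the reference standard, and most HPV-negative women are unverified. This is a real limit on absolute sensitivity, but a negligible one for specificity: even if 5% of HPV-negative women had disease (10.5 cases), algorithm specificity would be 1 − 18.0/267.9 = 93.3%.

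Fourth, the larger denominator compresses the contrast between algorithms about fourfold: 67.1% versus 94.4% becomes 91.9% versus 98.6%. The conditional estimates are therefore worth keeping alongside.

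**Conclusion.** The concern holds. Followed as written, the plan reports triage specificity under the algorithm's name, and it is too low whenever any woman without disease is HPV-negative. At PPV 49% the understatement is about 11-23 points for Pap and 4-25 points for VIA, using the cited sensitivity ranges as triage sensitivity and assuming no disease in HPV-negative women. With the cited specificities instead, it is about 1.5-17 points for Pap and 4-69 points for VIA. Planned sensitivity is sensitivity relative to HPV alone; it equals algorithm sensitivity only if HPV testing misses nothing. PPV, the sample size of 81 and the ranking of the two algorithms stand. This should be fixed before analysis, but it does not undermine the design.

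**What to change.** 1. Keep the HPV-positive-only estimates, labelled as triage sensitivity and specificity conditional on a positive HPV test.
2. For Aims 1 and 2, add algorithm specificity over all women HPV-tested. Count HPV-negative women as algorithm-negative, weight women with a colposcopy result up to all HPV-positive women, and give HPV-alone specificity on the same denominator. At s = 0.80, weighting changes the result from 94.0% (81 returners unweighted) to 93.5%. It assumes that returners are representative; non-returners may have a Pap result but will have no VIA result. State that most HPV-negative women lack the reference standard.
3. Vary HPV-missed disease as D × (1/Se − 1) with Se from 93% to 100%, which is 0-0.8% of HPV-negative women on the plan's inputs. Label any wider range as an assumption beyond the documents; 5%, for example, implies an HPV sensitivity of 21.6/32.1 = 67%.
4. Report sensitivity as relative to HPV alone, and say that it bounds absolute algorithm sensitivity from above.

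Optionally, if consent and approvals allow, use histology from HPV-negative women already referred for an abnormal Pap smear as a lower bound on HPV-missed disease. HPV-negative women with a normal Pap smear would remain unverified.

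Items 1-4 cost some wording and a short calculation on data already collected, with no added procedures. The sensitivity claim becomes less favourable. The optional step may need ethics coverage.
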